### Cerebro-vascular disease (stroke/TIA)

Terms	ICD10	ICD9C M	Read Codes	ICPC
Stroke, not specified as haemorrhage or infarction	I64			
Stroke NOS	I63.9			K90
Cerebrovascular accident			X00D1	
Stroke and cerebrovascular accident unspecified			XE2aB	
Stroke NOS			XaEGq	
Cerebrovascular Disease		430-432 (Except 432.1 "Subdural hemorrhage") 433- 435* 436, 437*, 438		
Sequelae of stroke, not specified as haemorrhage or infarction *	I69.4			
Sequelae of stroke, not specified as haemorrhage or infarction *			Gyu6C	
CVA - Extension of cerebrovascular accident			Xa1hE	
Lacunar stroke			X00DA	
Brain stem stroke syndrome	G46.3		G663.	
Cerebellar stroke syndrome	G46.4		G664.	
Personal history of stroke *			ZV125	
Sequelae of stroke NOS *	I69.3			
Stroke of uncertain pathology			X00DR	
TACI - Total anterior cerebral circulation infarction			X00D6	
PACI - Partial anterior cerebral circulation			X00D7	
Anterior circulation stroke of uncertain pathology			X00DS	
Posterior circulation stroke of uncertain pathology			X00DT	
Transient cerebral ischaemic attack, unspecified	G45.9			
TIA - Transient ischaemic attack			XE0VK XaEGK	
Other transient cerebral ischaemic attacks and related syndromes	G45.8		Fyu55	
Vertebro-basilar artery syndrome	G45.0			
Carotid artery syndrome	G45.1			
Multiple and bilateral precerebral artery syndromes	G45.2			
Transient ischemic attack (TIA), and cerebral infarction without residual deficits (personal history)*		V12.54		
Subarachnoid haemorrhage			G60..00	
Ruptured berry aneurysm			G600.00	

Terms	ICD10	ICD9C M	Read Codes	ICPC
Subarachnoid haemorrhage from carotid siphon and bifurcation			G601.00	
Subarachnoid haemorrhage from middle cerebral artery			G602.00	
Subarachnoid haemorrhage from anterior communicating artery			G603.00	
Subarachnoid haemorrhage from posterior communicating artery			G604.00	
Subarachnoid haemorrhage from basilar artery			G605.00	
Subarachnoid haemorrhage from vertebral artery			G606.00	
Subarachnoid haemorrhage from intracranial artery, unspecified			G60X.00	
Subarachnoid haemorrhage NOS			G60z.00	
Intracerebral haemorrhage			G61..00	
CVA - cerebrovascular accident due to intracerebral haemorrhage			G61..11	
Stroke due to intracerebral haemorrhage			G61..12	
Cortical haemorrhage			G610.00	
Internal capsule haemorrhage			G611.00	
Basal nucleus haemorrhage			G612.00	
Cerebellar haemorrhage			G613.00	
Pontine haemorrhage			G614.00	
Bulbar haemorrhage			G615.00	
External capsule haemorrhage			G616.00	
Intracerebral haemorrhage, intraventricular			G617.00	
Intracerebral haemorrhage, multiple localized			G618.00	
Intracerebral haemorrhage in hemisphere, unspecified			G61X.00	
Left sided intracerebral haemorrhage, unspecified			G61X000	
Right sided intracerebral haemorrhage, unspecified			G61X100	
Intracerebral haemorrhage NOS			G61z.00	
Other and unspecified intracranial haemorrhage			G62..00	
Intracranial haemorrhage NOS			G62z.00	
[X]Other subarachnoid haemorrhage			Gyu6100	
[X]Other intracerebral haemorrhage			Gyu6200	
[X]Subarachnoid haemorrhage from intracranial artery, unspecified			Gyu6E00	
[X]Intracerebral haemorrhage in hemisphere, unspecified			Gyu6F00	
Perinatal subarachnoid haemorrhage			Q412.00	
Evacuation of haematoma from temporal lobe of brain *			7004100	
Evacuation of haematoma from cerebellum *			7004200	
Evacuation of intracerebral			7004300	

Terms	ICD10	ICD9C M	Read Codes	ICPC
haematoma NEC *				
Aspiration of haematoma of brain tissue *			7008200	
[X]Subarachnoid haemorrhage from other intracranial arteries			Gyu6000	
[X]Sequelae of other nontraumatic intracranial haemorrhage *			Gyu6B00	
Sequelae of subarachnoid haemorrhage *			G680.00	
Sequelae of intracerebral haemorrhage *			G681.00	
Sequelae of other nontraumatic intracranial haemorrhage *			G682.00	
H/O sub-arachnoid haemorrhage *			14AF.00	
Subarachnoid haemorrhage			G60..00	
Infarction - precerebral			G63..11	
Cerebral infarct due to thrombosis of precerebral arteries			G63y000	
Cerebral infarction due to embolism of precerebral arteries			G63y100	
Infarction - cerebral			G64..12	
Stroke due to cerebral arterial occlusion			G64..13	
Cerebral infarction due to thrombosis of cerebral arteries			G640000	
Cerebral infarction due to embolism of cerebral arteries			G641000	
Cerebral infarction NOS			G64z.00	
Brainstem infarction NOS			G64z.11	
Cerebellar infarction			G64z.12	
Brainstem infarction			G64z000	
Left sided cerebral infarction			G64z200	
Right sided cerebral infarction			G64z300	
Infarction of basal ganglia			G64z400	
Pure motor lacunar syndrome			G665.00	
Pure sensory lacunar syndrome			G666.00	
Cereb infarct due cerebral venous thrombosis, nonpyogenic			G676000	
Cereb infarct due unsp occlus/stenos precerebr arteries			G6W..00	
[X]Cerebrl infarctn due/unspcf occlusn or sten/cerebrl artr			Gyu6300	
[X]Other cerebral infarction			Gyu6400	
[X]Cereb infarct due unsp occlus/stenos precerebr arteries			Gyu6G00	
Lateral medullary syndrome			G64z111	
Cerebrl infarctn due/unspcf occlusn or sten/cerebrl artr			G6X..00	
Sequelae of cerebral infarction *			G683.00	
Sequelae of stroke,not specfd as h'morrhage or infarction *			G68X.00	
Cereb infarct due unsp occlus/stenos precerebr arteries			G6W..00	
H/O: CVA/stroke *			14A7.00	
H/O: CVA *			14A7.11	
H/O: stroke *			14A7.12	

Terms	ICD10	ICD9C M	Read Codes	ICPC
H/O: Stroke in last year *			14AK.00	
Stroke and cerebrovascular accident unspecified			G66..00	
CVA unspecified			G66..11	
Stroke unspecified			G66..12	
CVA - Cerebrovascular accident unspecified			G66..13	
Brain stem stroke syndrome			G663.00	
Cerebellar stroke syndrome			G664.00	
Left sided CVA			G667.00	
Right sided CVA			G668.00	
CVA - cerebrovascular accident in the puerperium			L440.11	
[X]Other transient cerebral ischaemic attacks+related syndroms			Fyu5500	
Transient cerebral ischaemia			G65..00	
Transient ischaemic attack			G65..12	
Vertebrobasilar insufficiency			G656.00	
Other transient cerebral ischaemia			G65y.00	
Transient cerebral ischaemia NOS			G65z.00	
Impending cerebral ischaemia			G65z000	
Intermittent cerebral ischaemia			G65z100	
Transient cerebral ischaemia NOS			G65zz00	
Acute cerebrovascular insufficiency NOS			G671000	
Basilar artery syndrome			G650.00	
Insufficiency - basilar artery			G650.11	
Vertebral artery syndrome			G651.00	
Vertebro-basilar artery syndrome			G651000	
Carotid artery syndrome hemispheric			G653.00	
Multiple and bilateral precerebral artery syndromes			G654.00	
Drop attack			G65..11	
Cerebral infarction	I63			
Sequelae of cerebral infarction*	I69.3			
Sequelae of intracerebral haemorrhage*	I69.1			
Transient cerebral ischaemic attacks and related syndrome	G45			
Intracerebral haemorrhage	I61			
Vascular syndromes of brain in cerebrovascular diseases	G46			
Vertebro-basilar insufficiency			G65..13	
Wallenberg syndrome			G64Z100	
Personal history of stroke / cerebrovascular accident*			ZV12511 ZV12512	

\* Not to be used for the identification of new (incident) events but just for the characterization of baseline patient characteristics (history of).

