## 6. MILESTONES

Milestone	Planned date
Protocol submission to EMA	by 30 June 2014
Protocol approval by EMA	March 2015 *
Contract signature for study roll-out phase	April 2015*
Registration in the EU PAS register	April 2015*
Start of data collection	April 2015*
Statistical Analysis Plan	May 2015
End of data collection	End of June 2015
PSUR Update 1	October 2015
Start of data collection (second wave)	April 2016
End of data collection (second wave)	End of June 2016
PSUR Update 2	October 2016
Start of data collection (third wave)	April 2017
End of data collection (third wave)	End of June 2017
PSUR Update 3	October 2017
Final report of study results	End of November 2017

*\*Delay will impact the subsequent dates*

Milestones have been planned to maximise the efficiency and availability of data retrieval from the different data sources. A summary of such information is provided here:

Data source (Country)	Periodicity of updates	Time of the year when updates are released	Data availability for each update
SIDIAP (Spain)	Yearly	April-May	End (December 31 st ) of previous calendar year
IPCI (NL)	Yearly (twice is possible)	April-May	Variable as GPs provide not all at same time
THIN (UK)	Three times per year	Irregular	Variable as GPs provide not all at same time
HSD (Italy)	Every 6 months	June and December	End of previous calendar year (in June); up to June in December.
AUH (Denmark)	Yearly	May	December 31st the previous year

Both national regulations and prescribing practices have changed throughout the participating databases in recent months. As a consequence, in Italy, where GPs in primary care are not allowed anymore to initiate or renew strontium ranelate treatment since December 2013, the number of incident strontium ranelate users in the assessment period is expected to be null or very low. This point will be assessed for the first PSUR update (October 2015) as part of the analyses of the utilization patterns at population level (see [section 9.7.2.1](#)).

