### 9.2.5.3. Comparative safety study

Patients with any of the newly defined contra-indications will be excluded:

1. Established, current or past history of ischemic heart disease (IHD),
2. Peripheral arterial disease (PAD),
3. Cerebrovascular disease (CVD),
4. Uncontrolled hypertension, defined by MAH using an operational definition as follows: a patient will be defined as 'uncontrolled hypertension' if the 3 following conditions apply:
  - a. There is a previous diagnosis of hypertension coded in electronic medical records.
  - b. There is documented use of any anti-hypertensive therapy (either at that time or in the previous year before SR/BP initiation).
  - c. There are at least two readings of Systolic Blood Pressure  $\geq 150$  or Diastolic Blood Pressure  $\geq 95$  mmHg recorded in the 3 months prior to SR/BP initiation.

Also, eligible patients with a diagnosis of Paget's disease of bones will be excluded. And for the outcome VTE we will exclude patients with a previous VTE.

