### 9.3.2. Contra-indications and new indications

#### CONTRA-INDICATIONS

- History of Ischemic heart disease (IHD): myocardial infarction, angina pectoris, coronary artery bypass surgery (diagnoses or nitrate use) in year prior to SR therapy initiation.
- History of Peripheral arterial disease (PAD) in year prior to SR therapy initiation.
- History of transient ischemic attack (TIA) or stroke (ischemic or haemorrhagic) in year prior to SR therapy initiation.
- Uncontrolled hypertension, defined by MAH as the combination of the following: 1.previous diagnosis of hypertension coded in electronic medical records; 2.documented use of any anti-hypertensive therapy (either at that time or in the previous year before SR therapy initiation); and 3. at least two readings of Systolic Blood Pressure  $\geq 150$  or Diastolic Blood Pressure  $\geq 95$  mmHg recorded in the 3 months prior to SR therapy initiation.
- History of thromboembolic events (pulmonary embolism and deep venous thrombosis) in year prior to SR therapy initiation.

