#### Myocardial infarction / angina pectoris / aorto-coronary bypass surgery

Terms	ICD10 (SIDIAP, Aarhus hospital outpatients)	ICD9CM (HS, Aarhus hospital admissions)	Read Codes (THIN UK)	ICPC (IPCI)
Cardiac infarction	I22 I21			
MI - Myocardial infarction			X200E	
Acute myocardial infarction	I21		G30.. XE0Uh	K75
Acute myocardial infarction, unspecified	I21.9	410.9		
Myocardial infarction (acute) NOS	I21.3	410		
Acute myocardial infarction, unspecified site, episode of care unspecified		410.90		
AMI NOS, unspecified		410.90		
Acute myocardial infarction, subendocardial infarction		410.7	G32..	
Old myocardial infarction*	I25.2	412		
Healed myocardial infarction*			XE2aA G32.11	
Old myocardial infarction*			XE2aA	
Subsequent/recurrent myocardial infarction	I22		G35..	
Subsequent myocardial infarction of unspecified site	I22.9		Gyu36	
Subsequent myocardial infarction of other sites	I22.8		Gyu35 G353.	
Subsequent myocardial infarction of anterior wall	I22.0		G350. GYU3600	
Subsequent myocardial infarction of inferior wall	I22.1		G351.]	
Subsequent acute subendocardial myocardial infarction	I22.2			
Subsequent nontransmural myocardial infarction NOS	I22.2			
Subsequent myocardial infarction (acute) NOS	I22.9			
Reinfarction of myocardium			G35..	
Acute subendocardial myocardial infarction	I21.4		G307.00	
Acute myocardial infarction, subendocardial infarction, episode of care unspecified		410.70		

Terms	ICD10 (SIDIAP, Aarhus hospital outpatients)	ICD9CM (HS, Aarhus hospital admissions)	Read Codes (THIN UK)	ICPC (IPCI)
Nontransmural myocardial infarction	I21.4			
Acute myocardial infarction, of anterolateral wall		410.0	G300.	
Acute anteroseptal myocardial infarction			G3011	
Acute inferior myocardial infarction		410.4	X200K	
Acute myocardial infarction, true posterior wall infarction		410.6		
True posterior myocardial infarction			G306.	
Acute myocardial infarction, of inferoposterior wall		410.3	G303.]	
Other specified anterior myocardial infarction			G301.]	
Acute transmural myocardial infarction of unspecified site	I21.3		Gyu34	
Acute transmural myocardial infarction of anterior wall	I21.0 122.0			
Acute transmural myocardial infarction of inferior wall	I21.1 I21.11 I21.19 122.1			
Acute transmural myocardial infarction of other sites	I21.2 I21.21 I21.29 122.8			
ECG: old myocardial infarction*			3232.	
Anterior myocard.infarct NOS		410.8	G301z	
Other acute myocardial infarct			G30y.	
Other acute myocardial inf.NOS			G30yz	

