### Hypertension only if uncontrolled

Terms	ICD10	ICD9CM	Read Codes	ICPC
Hypertension	I10 I11 I12 I13 I15	401* 402* 403* 404* 405* 362.11 437.2	6627.00	K86 K87
			6628.00	
			6629.00	
			14A2.00	
			38DE.00	
			662b.00	
			662c.00	
			662d.00	
			662F.00	
			662G.00	
			662H.00	
			662O.00	
			662P000	
			662q.00	
			662r.00	
			67H8.00	
			7Q01.00	
			7Q01y00	
			8B26.00	
			8BL0.00	
8CR4.00				
8I3N.00				
F421300				
G2...00				
G2...11				
G20..00				
G200.00				
G201.00				
G202.00				

Terms	ICD10	ICD9CM	Read Codes	ICPC
			G203.00	
			G20z.00	
			G20z.11	
			G21..00	
			G210.00	
			G210000	
			G210100	
			G211.00	
			G211000	
			G211100	
			G21z.00	
			G21z000	
			G21z011	
			G21z100	
			G21zz00	
			G22..00	
			G220.00	
			G221.00	
			G222.00	
			G22z.00	
			G22z.11	
			G23..00	
			G230.00	
			G231.00	
			G232.00	
			G233.00	
			G23z.00	
			G24..00	
			G240.00	
			G240000	
			G240z00	
			G241.00	
			G241000	
			G241z00	
			G244.00	
			G24z.00	
			G24z000	
			G24zz00	
			G2y..00	
			G2z..00	
			G672.00	
			Gyu2.00	
			Gyu2000	
			Gyu2100	
			L122.00	
			L122000	
			L122100	
			L122300	
			L122z00	
			L127z00	
			L128.00	
			L128200	
			Lyu1.00	

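### The cerebrovascular contraindication is defined three ways and coded with different breadth by database, so its prevalence and the cohort without contraindications are not comparable across data sources

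*Protocol*

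**What the plan says.** All references are to the Protocol.

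**Definition**
- Section 9.3.2 gives the contraindication as "History of transient ischemic attack (TIA) or stroke (ischemic or haemorrhagic) in year prior to SR therapy initiation".
- Section 9.2.5.3 lists as an exclusion for the comparative safety study "Cerebrovascular disease (CVD"), with no restriction to stroke or TIA. Section 7.2 describes the regulatory restriction in the same broader terms.
- The code table in section 14.3.2 carries both terms in its heading.

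**Codes (section 14.3.2)**
- ICD-9-CM: one row for cerebrovascular disease as a whole. It starts with 430-432, whose only stated exception is 432.1 (subdural haemorrhage), and continues "433- 435* 436, 437*, 438". A personal-history code is listed separately.
- ICD-10: I61, I63, I64, I69.1, I69.3, I69.4, G45 and the whole of G46.
- Read: a long list of named strokes, haemorrhages, infarctions, TIAs and sequelae, including "Subarachnoid haemorrhage from carotid siphon and bifurcation" and other subarachnoid rows.
- ICPC: K90 only, on the unspecified-stroke row.
- Column headers name the databases only in the myocardial infarction table, where the ICD-9-CM column is "ICD9CM (HS, Aarhus hospital admissions").
- The hypertension table lists, under ICD-9-CM, "401* 402* 403* 404* 405* 362.11 437.2".

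**Use**
- Contraindication prevalence in three periods is a primary objective (section 8). Section 9.7.2.2 runs the time series separately in each data source. Section 9.7.4 pools all estimates and adds a mega-pooled analysis. Section 9.7.5 repeats the work without Spain.
- For Italy, section 6 says that "the number of incident strontium ranelate users in the assessment period is expected to be null or very low".

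**The concern.** A contraindication whose prevalence is a primary outcome should mean the same in every database. Here a patient with the same history could count as contraindicated in one source and not in another. Three things are affected.

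- **Prevalence by country.** Part of any difference between countries would reflect code lists.
- **Strata and cohort.** Section 9.7.3.2 stratifies event rates by number of contraindications, and section 9.9 relies on restriction to patients without them as a control for confounding. Both would select different patients by source.
- **Pooled prevalence over time.** The ICD-9-CM block serves HSD, whose incident users are expected almost to disappear. If that block finds more patients, pooled prevalence loses its most broadly defined component just when the effect of the risk minimization measures is read.

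**Working it through.** **1. Are the columns equivalent?**

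| Source of definition | Breadth | Subarachnoid haemorrhage | TIA |
|---|---|---|---|
| Section 9.3.2 | TIA or stroke, ischaemic or haemorrhagic | in, as haemorrhagic stroke | in |
| Section 9.2.5.3 | cerebrovascular disease | in | in |
| ICD-9-CM | 430-438 block less 432.1 | not among the stated exceptions | not among the stated exceptions |
| ICD-10 | mainly stroke/TIA, plus G46 | no row | G45 |
| Read | mainly stroke/TIA, some wider terms | many rows | many rows |
| ICPC | K90 only | no code on those rows | no code on those rows |

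They are not equivalent. The document itself shows that the ICD-9-CM block goes beyond stroke/TIA: 437 is taken with an asterisk and no exception, yet 437.2 also appears as a hypertension code.

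The asterisks on 435 and 437 do not narrow the baseline definition. Read as the table's footnote, they bar use for incident events but keep the codes as history. Read as wildcards, they widen the list.

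**2. The plan's own figures.** The only stated sizes that use this contraindication are the precision figures in section 9.5.1: n = 1.96² × p(1 − p) / 0.05².
- Men, p = 0.295: 319.6, so 320 (stated 320).
- Women, p = 0.192: 238.4, so 239 (stated 239).

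Both reproduce. They concern MI, CVD and PAD combined.

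**3. Italy's weight, from Table (9.5) 1 (2012 counts)**
- Incident: 1,209 / 5,819 = 20.8%. Without Spain: 1,209 / (5,819 − 4,008) = 1,209 / 1,811 = 66.8%.
- Prevalent: 10,129 / 27,764 = 36.5%. Without Spain: 10,129 / (27,764 − 14,502) = 10,129 / 13,262 = 76.4%.

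Italian men and women add to 10,229, not 10,129. Using sex-specific sums throughout gives 36.7% instead of 36.5%, which changes nothing here.

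**4. Size of a possible artefact in the crude pool.** Let w be Italy's share, p the prevalence under a common definition, and e the Italian excess in percentage points due only to the wider codes. Pooled prevalence before is w(p + e) + (1 − w)p = p + we. If Italy falls to zero, it becomes p. The fall is w × e.

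The protocol gives no value for e, so a range is assumed:

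| Assumed e (points) | Incident | Prevalent | Incident, no Spain | Prevalent, no Spain |
|---|---|---|---|---|
| 1 | 0.21 | 0.36 | 0.67 | 0.76 |
| 2 | 0.42 | 0.73 | 1.34 | 1.53 |
| 5 | 1.04 | 1.82 | 3.34 | 3.82 |
| 10 | 2.08 | 3.65 | 6.68 | 7.64 |

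A fall as large as the planned ±5-point precision needs e = 5 / w: about 24 points (incident) or 14 (prevalent) with all countries, and about 7.5 or 6.5 without Spain.

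**5. Inverse-variance pooling.** With fixed-effect weights n / [p(1 − p)], all countries, p of 3% to 10% and e of 2 to 10 points, the fall is 0.3 to 1.3 points (incident) or 0.5 to 2.4 points (prevalent). The effect is smaller because the higher-prevalence database gets less weight.

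**The case against.** **The main analyses are protected.** The time series runs within each source, and a wide list that stays constant within HSD creates no change there. Cases and controls are matched within data source, so different exclusion lists do not by themselves confound strontium ranelate against bisphosphonates. This stands. It does not cover by-period pooled prevalence, the mega-pooled prevalence, country comparisons or the contraindication-count strata.

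**The lists are provisional.** Sections 9.6 and 14.3.2 promise discussion with partners before extraction, and sections 9.6 and 9.6.4 promise harmonisation and benchmarking. This partly stands. However, the benchmark compares incidence rates, and codes kept only as history are not incident events, so it may miss exactly these differences. Section 9.6 also says the lists already followed consensus with partners.

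**Database-specific coding is deliberate.** Section 9.6 rules out one extraction algorithm for all sources. That justifies different codes, but not different clinical concepts.

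**The contrast is not Italy against the rest.** This stands. The ICD-9-CM column also serves Aarhus hospital admissions, although Table (9.4) 1 lists Aarhus as ICD-10. ICD-10 has G46, and Read has wider terms such as drop attack and acute cerebrovascular insufficiency. In IPCI, free text (sections 9.4.1 and 9.6.1) may partly make up for the missing TIA code, and IPCI has only 42 of the 5,819 incident users.

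**The broad row may be the intended one.** Sections 7.2 and 9.2.5.3 both speak of cerebrovascular disease. This stands, so the documents do not settle which column should move.

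**Conclusion.** The inconsistency is established from the text: sections 9.2.5.3 and 9.3.2 and the code columns do not describe one contraindication. As written, its prevalence, the count strata and the cohort without contraindications differ in meaning by database.

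A reader might infer that pooled prevalence will fall artificially and look like success of the measures. For example, if the broad block found twice as many patients in Italy, the relative fall would be w / (1 + w), about 17% (incident) and 27% (prevalent). The documents do not support this as a prediction. They give no yield for the broad block against stroke/TIA codes. The weights come from 2012 alone, whereas the reference period starts in 2004 (2006 for SIDIAP). The near-zero expectation is stated only for incident Italian users; for prevalent users it is an inference from the bar on renewal by GPs.

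What holds is conditional: a fall of w × e points in crude pooled estimates, with e unknown. The exposure is greatest in the planned analysis without Spain, where Italy is two thirds or more of 2012 users. A bias in the matched safety comparison is not shown.

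**What to change.** Before extraction:

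1. Choose one definition, either stroke/TIA or any cerebrovascular disease. State it identically in sections 9.2.5.3 and 9.3.2 and in the table heading of section 14.3.2.
2. Apply it in every coding column. For stroke/TIA, narrow the ICD-9-CM block. For any cerebrovascular disease, widen ICD-10, Read and ICPC. Either way, fill the ICD-10 subarachnoid haemorrhage and ICPC TIA gaps, say whether 437.2 counts as cerebrovascular disease, hypertension or both, and say what the asterisks in the ICD-9-CM row mean. Partners should confirm the exact codes.
3. Reconcile the coding system stated for Aarhus admissions between Table (9.4) 1 and section 14.3.2.
4. Report pooled by-period prevalence with and without Italy, or standardised to a fixed mix of the databases that contribute users in all three periods. Do this in the analysis without Spain as well.

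The cost is a code-list edit and a small amount of extra analysis, with no new data. Cerebrovascular prevalence will change in some databases compared with the present lists.
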